8.2 Clinical laboratory evaluation

Laboratory values (chemistry, hematology, coagulation profile, and urinalyses) will be numerically described by visit for observed values and change from baseline by treatments (each KHK4083 dose level versus placebo). The numbers and percentages of subjects with high, normal and low laboratory results will be also summarized for each visit by treatments (Placebo, 1.0 mg/kg, 3.0 mg/kg, and 10 mg/kg) and treatment periods (“Double-Blind Therapy Period and Double-Blind Therapy Follow-up Period” and “OLE Therapy Period and OLE Therapy Follow-up Period”). For the laboratory values which have the normal (e.g., below/within above the normal range) or categorical result (e.g., -/±/+), shift tables will display the cross tabulation of the baseline versus the results of the post-baseline by treatments (Placebo, 1.0 mg/kg, 3.0 mg/kg, and 10 mg/kg) and treatment periods (“Double-Blind Therapy Period and Double-Blind Therapy Follow-up Period” and “OLE Therapy Period and OLE Therapy Follow-up Period”).

Means with SDs for numeric parameters among lab values at all visits will be performed graphically by treatments. Mean changes from Baseline will also be performed in the same manner.

Data listings will be generated of all safety lab values that are outside of the normal range. Listing will also be prepared for multiplex-31 assay data.

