ALT=alanine aminotransferase; AST=aspartate aminotransferase; BUN=blood urea nitrogen; β-HCG=beta human chorionic gonadotrophin; ; FSH=follicle-stimulating hormone; HIV=human immunodeficiency virus; IGRA=interferon gamma release assay; LDH=lactate dehydrogenase; LTE=long-term extension; OLE=open-label extension; PD=pharmacodynamic(s); PPD=purified protein derivative; RBC=red blood cell; RNA=ribonucleic acid; RT-PCR=Real-time reverse transcription-polymerase chain reaction; SGOT=serum glutamic-oxaloacetic transaminase; SGPT=serum glutamic-pyruvic transaminase; TB=tuberculosis; US=United States; WBC=white blood cell; wr-CRP=wide-range C-reactive protein.

Any clinically important abnormal laboratory values noted at the Screening visit will be recorded as medical history. In addition, in order for the Sponsor to collect additional information about clinically important laboratory abnormalities, at minimum, the following laboratory abnormalities should be captured as appropriate:

- Any laboratory test result that meets the criteria for an SAE;
- Any laboratory abnormality that requires the subject to have study treatment discontinued or interrupted;
- Any laboratory abnormality that requires the subject to receive specific corrective therapy.

All clinically important abnormal laboratory tests occurring during the study will be repeated at appropriate intervals until (1) the value returns to baseline, (2) the value is judged to be clinically acceptable by the Investigator and the Sponsor, or (3) a diagnosis that explains the

abnormal laboratory value is made. When possible, the Investigator should report the clinical rather than the laboratory term (e.g., anemia versus low hemoglobin).

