OLE Therapy Period								
OLE Therapy Period and OLE Therapy Follow-up Period								

1) Double-Blind Therapy Period includes both Double-Blind Induction Therapy Period and LTE Therapy Period.

2) Double-Blind Therapy Follow-up Period includes both Follow-up Periods after Double-Blind Therapy Period and LTE Therapy Period.

3) For subjects randomized to Placebo, they receive 4083 administration during the duration but they are summarized as one category as "Placebo".

Image which shows the relationship between summary pattern and data will be displayed in Figure 4.

Figure 4 Summary Patterns

Forms

Title Statistical Analysis Plan Template

Code

Version

Effective Date

[figure not shown]
Page

FRM_ST03_032

01

23 Apr 2015

21 of 53

General reporting conventions will include the following:

- The baseline value for any measurement is the last value obtained prior to receiving administration of KHK4083 or placebo on Day 1 at Week 0. All nominal time points will be used for analysis; actual assessment times will not be used to reclassify the time point at which a measure was taken.

	Forms			
	Title	Statistical Analysis Plan Template		
	Code	Version	Effective Date	Page
	FRM_ST03_032	01	23 Apr 2015	22 of 53

- Study day: Study day will be calculated relative to the date of KHK4083 or placebo administration (Day 1) as:
 - (If Date of event \geq Date of first investigational product administration) Date of event – Date of first investigational product administration + 1 and
 - (If Date of event $<$ Date of first investigational product administration) Date of event – Date of first investigational product administration

This formula will be used when calculating days to a specific event (i.e., concomitant medication and/or AE start date). A negative study day indicates an event prior to investigational product administration.

- Unless otherwise noted, all percentages will be presented to one decimal place.
- Individual data listings of all data represented on the eCRF will be provided as an appendix to facilitate investigation of the tabulated values and to allow for the clinical review of all variables. All data listings will be sorted by dose Cohort, site-subject number, visit, and time points where appropriate.
- Post-dose data from unscheduled visits will be excluded from the summary tables but included in the data listings.

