8.4 ECGs

Electrocardiogram measurements include heart rate (beats/min), RR interval (msec), PR interval (msec), QRS duration (msec), QT interval (msec), QTc interval (msec) and ECG interpretation. A standard 12-lead ECG will be performed at Screening; during Induction Therapy (predose and at the end of infusion) on Day 1 (Baseline, Week 0), Week 8, and Week 10 and at Week 52 of OLE/LTE Therapy Period. The ECGs will be recorded after the subject has rested for approximately 5 minutes in a supine position.

	Forms			
	Title	Statistical Analysis Plan Template		
	Code	Version	Effective Date	Page
	FRM_ST03_032	01	23 Apr 2015	36 of 53

Summary statistics for the actual ECG parameter values and change from baseline will be provided for each visit. The number and percentage of subjects with elevated QTcF values (> 450 msec, > 480 msec, and > 500 msec) at each scheduled visit (time point) and overall for all post-baseline visits will be presented by treatments (each KHK4083 dose level versus placebo). In addition, the number and percentage of subjects with QTcF values that increase by > 30 msec and > 60 msec from baseline will be presented by treatments at each scheduled visit (time point) and overall for all post-baseline visits. QTcF will be calculated by the Fridericia formula that “(QTcF = QT/(RR)^{1/3})”.

A shift table from baseline to the worst post-baseline values during the treatment period will be provided for QTcF interval. Both scheduled and unscheduled visits during the treatment period will be considered. The following categories will be used: ≤ 450 msec, > 450 and ≤ 480 msec, > 480 and ≤ 500 msec, and > 500 msec.

The numbers and percentages of subjects with reported ‘Abnormal, Clinically Significant Change’ ECG results will be also summarized for each visit by treatments (Placebo, 1.0 mg/kg, 3.0 mg/kg, and 10 mg/kg) and treatment periods (“Double-Blind Therapy Period and Double-Blind Therapy Follow-up Period” and “OLE Therapy Period and OLE Therapy Follow-up Period”).

All ECG parameters will be presented in data listings.

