Table 14.3.1-5.3	Treatment-Emergent Adverse Events Leading to Discontinuation from The Study By System Organ Class and Preferred Term During Open-Label Extension Therapy Period and Open-Label Extension Therapy Follow-Up Period / Safety Analysis Set
Table 14.3.4-1.1	Vital Signs and Body Weight and Change from Baseline During Double-Blind Therapy Period and Double-Blind Therapy Follow-Up Period / Safety Analysis Set
Table 14.3.4-1.2	Vital Signs and Body Weight and Change from Baseline During Open-Label Extension Therapy Period and Open-Label Extension Therapy Follow-Up Period / Safety Analysis Set
Table 14.3.4-2.1	Summary of Clinical Laboratory Values-Hematology During Double-Blind Therapy Period and Double-Blind Therapy Follow-Up Period / Safety Analysis Set
Table 14.3.4-2.2	Summary of Clinical Laboratory Values-Hematology During Open-Label Extension Therapy Period and Open-Label Extension Therapy Follow-Up Period / Safety Analysis Set
Table 14.3.4-2.3	Summary of Clinical Laboratory Values- Serum Chemistry During Double-Blind Therapy Period and Double-Blind Therapy Follow-Up Period / Safety Analysis Set
Table 14.3.4-2.4	Summary of Clinical Laboratory Values- Serum Chemistry During Open-Label Extension Therapy Period and Open-Label Extension Therapy Follow-Up Period / Safety Analysis Set
Table 14.3.4-2.5	Summary of Clinical Laboratory Values- Coagulation Profile During Double-Blind Therapy Period and Double-Blind Therapy Follow-Up Period / Safety Analysis Set
Table 14.3.4-2.6	Summary of Clinical Laboratory Values- Coagulation Profile During Open-Label Extension Therapy Period and Open-Label Extension Therapy Follow-Up Period / Safety Analysis Set

Forms

Title Statistical Analysis Plan Template

Code	Version	Effective Date	Page
FRM_ST03_032	01	23 Apr 2015	46 of 53

Number	Title
Table 14.3.4-2.7	Summary of Clinical Laboratory Values- Urinalyses During Double-Blind Therapy Period and Double-Blind Therapy Follow-Up Period / Safety Analysis Set
Table 14.3.4-2.8	Summary of Clinical Laboratory Values- Urinalyses During Open-Label Extension Therapy Period and Open-Label Extension Therapy Follow-Up Period / Safety Analysis Set
Table 14.3.4-2.9	Shift Table of Clinical Laboratory Values -Hematology During Double-Blind Therapy Period and Double-Blind Therapy Follow-Up Period / Safety Analysis Set

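### By-dose hematology tables leave out unscheduled values and do not define a worst-value shift, so a subject's lowest count may appear only in listings (minor, cheap to fix)

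*SAP*

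**What the plan says.** SAP 8.2 gives hematology four by-treatment outputs:

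- numeric summaries of observed values and change from baseline at each visit (SAP 4.1 adds that these include minimum and maximum);
- category counts: "The numbers and percentages of subjects with high, normal and low laboratory results will be also summarized for each visit by treatments";
- shift tables: "shift tables will display the cross tabulation of the baseline versus the results of the post-baseline by treatments";
- plots of means by visit.

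It also lists all out-of-range values. SAP 9.7 places the table shells in a separate document.

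Two general rules in SAP 4.1 apply: "Post-dose data from unscheduled visits will be excluded from the summary tables but included in the data listings", and, on nominal visits, "actual assessment times will not be used to reclassify the time point at which a measure was taken".

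Protocol 10.6.1 makes extra draws foreseeable: "All clinically important abnormal laboratory tests occurring during the study will be repeated at appropriate intervals".

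SAP 8.4 treats QTcF differently: "A shift table from baseline to the worst post-baseline values during the treatment period will be provided for QTcF interval", and "Both scheduled and unscheduled visits during the treatment period will be considered". It also sets numeric QTcF limits and counts subjects over all post-baseline visits.

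**The concern.** Safety and tolerability form the Part A primary objective, and Protocol 6.5.1 asks for careful monitoring of hematologic abnormalities. For a blood count, the usual questions about each dose are how low it went and in how many subjects. The tables as specified do not answer either fully, for three reasons.

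1. The shift table could be built on each visit, the last value or the worst value. The SAP does not say.
2. An unscheduled repeat cannot enter any laboratory summary, even if it is the subject's lowest value.
3. Normal-range categories do not show depth, and the visit minimum shows one extreme subject without showing how many others fell.

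At stake is the completeness of the final by-dose laboratory summary.

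**Working it through.** The plan states no figure to reproduce. The check sets the rules side by side and then gives a sense of scale. The documents give no event rate, so the blood counts below are assumed illustrations.

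**Where unscheduled values arise.** Protocol Tables 9-1 and 9-2 schedule hematology every 14 days from Week 2 to Week 12 and every 28 days from Week 12 to Week 52. A repeat drawn between those visits is unscheduled. Under SAP 4.1 it is neither summarized nor moved to a nearby visit.

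**What a repeat can hide.** Suppose neutrophils are 1400/mm3 at a scheduled visit and 600/mm3 at an unscheduled repeat. If 1400 is below the laboratory's range (assumed), the subject is counted as low at that visit, but the tables show 1400 and never 600. Depth is lost; the subject is not.

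**What normal-range categories can hide.** Suppose hemoglobin falls from 11 to 7 g/dL at a scheduled visit, with an assumed lower limit of normal of 12 to 13 g/dL. The shift is low to low. For that dose and visit, however, the minimum is at most 7 and the minimum change is at most 7 - 11 = -4. The fall is visible; the number of subjects with such a fall is not.

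**What by-visit counts can hide.** Take one low result among 9 subjects at each of three visits:

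- same subject each time: 1/9 = 11.1% ever low;
- three different subjects: 3/9 = 33.3% ever low.

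A shift built by visit cannot separate these. A shift built on the worst scheduled value would.

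**Which period a worst value should cover.** The listed title is "Shift Table of Clinical Laboratory Values -Hematology During Double-Blind Therapy Period and Double-Blind Therapy Follow-Up Period / Safety Analysis Set", so treatment and follow-up share one table. Scheduled post-baseline tests for an induction-only subject are:

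| | Induction | Follow-up | Follow-up share |
|---|---|---|---|
| Cohort 4 | 6 (Weeks 2 to 12) | 3 (Weeks 16, 20, 26) | 3/9 = 33.3% |
| Cohorts 1-3 | 8 (adds Days 2 and 8, Table 10.4.1-1) | 3 | 3/11 = 27.3% |

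Protocol 8.5.1 permits otherwise prohibited immunosuppressants in follow-up, so a single worst value over both periods mixes two situations. Dropping follow-up would also be wrong. With the simulated 10 mg/kg half-life of 26.2 days (Protocol Table 8.1.3-1) and simple exponential decline from the Week 10 dose:

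- Week 16 (42 days): 0.5^(42/26.2) = about 33% remaining;
- Week 20 (70 days): 0.5^(70/26.2) = about 16% remaining.

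A low point in early follow-up could still be drug-related, so the two periods should be shown separately.

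**Precision.** Exact two-sided 95% upper limits for zero events are 1 - 0.025^(1/9) = 33.6% for 0/9 and 1 - 0.025^(1/27) = 12.8% for 0/27. Any added table stays descriptive.

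**The case against.** The strongest case against is that very little is hidden.

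- A repeat under Protocol 10.6.1 follows a result already judged abnormal. That result will usually be scheduled, and if it is out of range it is counted. Only extra depth is missed, and only if the repeat is lower; it may equally show recovery.
- The deepest scheduled fall appears in the visit minimum and minimum change.
- All out-of-range values, scheduled or not, are listed by dose cohort, which is a short read with 9 active subjects per Part A cohort.
- Laboratory abnormalities that qualify as adverse events (Protocol 10.6.8) are tabulated by dose and maximum severity.
- The shells may already define the shift table.
- Protocol 12.5 asks for summary and shift tables, and the SAP supplies them.

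Most of this stands and sets the size of the point. Two things remain. Listings are not by-dose counts, and Protocol 10.6.5.2 grades event intensity by symptoms, interference with daily activities and need for treatment, so an asymptomatic low count could be graded mild or not reported as an event. The shells might settle which value the shift uses, but nothing in the SAP suggests that they override the SAP 4.1 exclusion, which SAP 8.4 does expressly for QTcF.

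A reader might infer that affected subjects disappear from the summaries, at 1/9 = 11.1% of a Part A active arm or 1/27 = 3.7% of the pooled recommended dose for each one. That requires a low count seen only at an unscheduled draw. The repeat rule does not normally produce this, and the documents give no basis for a rate.

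**Conclusion.** The point holds as a minor one. Under the SAP as written, a count that is lower at an unscheduled repeat enters no by-dose laboratory table, and no table is defined to show how many subjects per dose had a low or deeply reduced count at any time. If the shells build the shift on the worst scheduled value, the count of subjects ever low at scheduled visits would be available; the unscheduled and depth gaps would remain.

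The documents do not support a reading that subjects are less safe or that the dose choice is compromised. Counts are tested at every visit, the stopping criteria in Protocol 7.5.3 apply, and dose selection rests with the Safety Monitoring Committee and the sponsor. Nor do they support a conflict between protocol and SAP: Protocol 6.5.1 is an instruction on conduct, not on analysis. The conclusion rests on the SAP text alone and on repeats being recorded as unscheduled visits.

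**What to change.** In SAP 8.2, define the hematology shift table as baseline to each subject's lowest post-baseline value, using scheduled and unscheduled visits, and state this as an exception to SAP 4.1. Show the treatment period and the follow-up period separately, so that a late low point is kept without being mixed with on-treatment values.

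Add, by dose level and placebo, a descriptive summary of each subject's lowest value and largest fall from baseline for neutrophils, lymphocytes, platelets and hemoglobin. Counts below fixed limits are optional and the limits are the sponsor's choice. The entry limits in Protocol 7.3 (neutrophils 1500/mm3, platelets 100,000/mm3, hemoglobin 9 g/dL) are available but are not toxicity limits.

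The cost is one sentence and a few descriptive outputs from data already collected. The drawback is that retested subjects have more chances of a low value, and Cohorts 1-3 have 8 scheduled induction tests against 6 in Cohort 4. A footnote can say so, or a version limited to scheduled Weeks 2 to 12 can be shown for comparing doses in induction.

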8.3 Vital signs and body weight

Vital signs, including systolic and diastolic blood pressures (mm Hg), radial pulse rate (beats/min), and respiration rate (breaths/min), oral body temperature (degrees Celsius), and body weight (kg) will be summarized descriptively by time point of collection for the data as observed. Change from baseline results will be summarized in the same manner as the laboratory values.

8.4 ECGs

Electrocardiogram measurements include heart rate (beats/min), RR interval (msec), PR interval (msec), QRS duration (msec), QT interval (msec), QTc interval (msec) and ECG interpretation. A standard 12-lead ECG will be performed at Screening; during Induction Therapy (predose and at the end of infusion) on Day 1 (Baseline, Week 0), Week 8, and Week 10 and at Week 52 of OLE/LTE Therapy Period. The ECGs will be recorded after the subject has rested for approximately 5 minutes in a supine position.

	Forms			
	Title	Statistical Analysis Plan Template		
	Code	Version	Effective Date	Page
	FRM_ST03_032	01	23 Apr 2015	36 of 53

Summary statistics for the actual ECG parameter values and change from baseline will be provided for each visit. The number and percentage of subjects with elevated QTcF values (> 450 msec, > 480 msec, and > 500 msec) at each scheduled visit (time point) and overall for all post-baseline visits will be presented by treatments (each KHK4083 dose level versus placebo). In addition, the number and percentage of subjects with QTcF values that increase by > 30 msec and > 60 msec from baseline will be presented by treatments at each scheduled visit (time point) and overall for all post-baseline visits. QTcF will be calculated by the Fridericia formula that “(QTcF = QT/(RR)^{1/3})”.

A shift table from baseline to the worst post-baseline values during the treatment period will be provided for QTcF interval. Both scheduled and unscheduled visits during the treatment period will be considered. The following categories will be used: ≤ 450 msec, > 450 and ≤ 480 msec, > 480 and ≤ 500 msec, and > 500 msec.

The numbers and percentages of subjects with reported ‘Abnormal, Clinically Significant Change’ ECG results will be also summarized for each visit by treatments (Placebo, 1.0 mg/kg, 3.0 mg/kg, and 10 mg/kg) and treatment periods (“Double-Blind Therapy Period and Double-Blind Therapy Follow-up Period” and “OLE Therapy Period and OLE Therapy Follow-up Period”).

All ECG parameters will be presented in data listings.

8.5 Physical examination except body weight

The complete physical examination will include examination of all pertinent body systems while the subsequent physical examinations will include specific assessments of any changes from previous status and review of those organ systems as deemed appropriate for that subject. Physical examination results will be included in individual subject listings.

	Forms			
	Title	Statistical Analysis Plan Template		
	Code	Version	Effective Date	Page
	FRM_ST03_032	01	23 Apr 2015	37 of 53

9. Tables and Listings

9.1 Programs and tables quality control

The statistical programmer of the tables and listings will carefully review the programs and will verify that no error message is highlighted in the 'LOG' file. Moreover, a second statistical programmer will verify the internal consistency of each table by checking the results using different SAS programs.

The following level of validation will be implemented:

Validation of statistical datasets: independent programming, with a comparison of the results against the initial datasets.

Validation of statistical output: independent programming, with a comparison of the results against the initial output.

9.2 Programming conventions

All tables/listings will be presented in landscape format.

The standard font size is 9 points Courier New for all tables. Listings will be presented with an 8 or 7 points Courier New.

Titles will be center-aligned; footnotes will be left-aligned.

Each table/figure/listing will have 2 titles:

- The 1st title will be the table/figure/listing number with the description of the table/figure /listing;
- The 2nd title will be a description of the study population presented in the table/figure/listing. Some tables will have another title (before 2nd title) with a description of the statistical method used in those tables.

Any footnote added to explain the table/listing/figure contents will be presented in the following format:

Note 1: Percentages are calculated on the number of subjects (N).

Note 2: A serious adverse event is an....

Note 3:

The last two footnotes of each table/figure will be footers indicating:

- the reference listing of the data;
- the program name, the date and time of generation and the SAS[®] version used.

The last footnote of each listing will be a footer indicating the program name, the date and time of generation and the SAS[®] version used.

	Forms			
	Title	Statistical Analysis Plan Template		
	Code	Version	Effective Date	Page
	FRM_ST03_032	01	23 Apr 2015	38 of 53

In the tables and listing the treatment under comparison will be labeled as “Cohort 1 1.0 mg/kg”, ‘Cohort 2 3.0 mg/kg’ “Cohort 3 10 mg/kg”, ‘Cohort 4 XX mg/kg’ (XX is the recommended dose) and “Placebo”.

In tables and figures, unless otherwise stated, the number of subjects corresponding to analysis set will be shown at the part of “N=XX” together with the labels of treatment group.

- For example, in Table 14.3.1-1.1 “Overall summary of treatment-emergent adverse events during study / safety analysis set”, the part of “N=XX” will display the number of subjects in safety analysis set corresponding to the labels of the treatment group (e.g. 1.0 mg/kg, 3.0 mg/kg, 10 mg/kg, Placebo) and All.

Unless otherwise stated, listings will be presented by randomized treatment, and sorted by cohort and the site-subject identifier.

Except for the listings 16.2.1-1.2 (based on screening failure subjects) and 16.2.1-1 (based on all subjects), all the listings will be based on the randomized subjects.

In all the listings on safety variables, a column with a flag (§) for treatment misallocation will identify the treatment misallocations.

The derived variables will be identified in the listings with a flag (*).

Tabular display of data for prior / concomitant medications, and all tabular displays of adverse event data should be presented by the body system, drug class, or SOC with the highest occurrence in the active treatment group (KHK4083 combined group) in decreasing order. Within the body system, drug class and SOC, medical history (by Preferred Term), drugs (by ATC1 code), and adverse events (by Preferred Term) should be displayed in decreasing order. If incidence for more than 1 term is identical, they should then be sorted alphabetically.

In general, dates will be presented on listings in the format ddmmyyyy (date9.) and time in the format hh:mm (time5.). In case of partial dates or times, missing information will be replaced by dashes. Numeric variables will be listed generally with the same number of decimal places as in the actual data.

The following rules on decimal places will be considered in the listings for the derived variables (in the analyses approximations will not be performed):

- Age (years), duration of treatment (days): 0 decimal place;
- Change from baseline: same as the variable considered.

The following rules on decimal places will be considered for the results of the analyses (if the analyses are performed on derived variables, the level of precision of the actual data is derived from the previous list):

- Min, max: same as actual data;
- Mean and its confidence limits (unadjusted and adjusted), adjusted difference between means and its confidence limits, SD, median: actual data + 1 decimal;
- Percentage: 1 decimal place.

	Forms			
	Title	Statistical Analysis Plan Template		
	Code	Version	Effective Date	Page
	FRM_ST03_032	01	23 Apr 2015	39 of 53

9.3 **Glucocorticoid**

Among concomitant medications which started to be administered from Day 1, those corresponding to the list below will be defined as glucocorticoid and considered in Tables and Listings relative to glucocorticoid.

- Medications that ATC code is “H02AB” (that is assigned to “Glucocorticoids”).

	Forms			
	Title	Statistical Analysis Plan Template		
	Code	Version	Effective Date	Page
	FRM_ST03_032	01	23 Apr 2015	40 of 53

